Subjects in Study 1 and Study 1504 if eligible could participate in this study, Study 1503, an open-label long-term, safety extension study. In a safety update of Study 1503 (cut-off date 14-Oct 2019, n=330 enrolled), the median percent change in CSF compared to baseline (core study) for the overall open-label Treatment period (Day 1 to End of Study [EOS]) was -66.8% (P_ <0.001). The reduction from baseline in monthly CSF observed at Month 1 of the open-label Treatment period was maintained through Month 24, the longest treatment duration included in the analysis. A total of 317/330 subjects reported at least 1 TEAE during the open-label Treatment period. The most common (≥ 10%) TEAEs reported during the open-label Study 1503 at the time of the cut-off date were blood glucose decreased, decreased appetite, diarrhea, ear infection, echocardiogram abnormal, influenza, nasopharyngitis, pyrexia, seizure, and upper respiratory tract infection. As in the double-blind studies, all of the echocardiogram abnormal TEAEs in Study 1503 were trace mitral or trace aortic valve regurgitation, which are not considered pathologic as stated in current guidelines on the use of ECHO for the assessment of valve function (Zoghbi 2017, Lancellotti 2010a, Lancellotti 2010b). At least 1 treatmentemergent SAE was reported by 80/330 (24.2%) subjects. The most frequently reported ($\geq 5\%$) SAE was seizure, occurring in 24/330 (7.3%) of subjects. A total of 176/330 subjects (53.3%) experienced at least 1 TEAE that was considered to be related to study treatment and 8/330 subjects (2.4%) reported at least 1 SAE that was considered to be related to study treatment. A total of 11/330 (3.3%) subjects discontinued due to a TEAE.

Please reference the ZX008 IB 2022 v.10.0 for more detailed information on the safety and efficacy of ZX008.

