3.3.1 Safety

The safety endpoints of the study are:

- Adverse Events (AEs)
- Laboratory safety (hematology, chemistry
- Vital signs (blood pressure, heart rate, temperature, and respiratory rate)
- Physical examination (if clinically indicated)
- Neurological examination (if clinically indicated) etiel
- ECGs (if clinically indicated)
- Doppler ECHOs
- Body weight/height
- Chest x-ray (subjects in France and Netherlands [NL] only)
- EEG (in Italy only)

Laboratory safety parameters (hematology, biochemistry) and physical/neurological examinations will only be assessed as clinically indicated. In all countries except France, ECGs will only be assessed as clinically indicated. In France, only the ECGs at clinic visits 1 and 13 and chest x-rays at clinic visits 3, 5, 7, 9, and 11 will be assessed as clinically indicated; these assessments are required at the other clinic visits. Further, chest x-rays will be collected only in France and NL, and in the latter, only when clinically indicated. EEGs will be collected only in Italy, and only when clinically indicated.

3.3.2 **Efficacy**

The effectiveness endpoints of the study are:

- Percent improvement in seizure burden as assessed by the investigator (or designee)
- CGI-I, globally and for specific domains, as assessed by investigator (or designee)

Zogenix International Limited, a wholly owned subsidiary of UCB 27 October 2023 Statistical Analysis Plan Fenfluramine Hydrochloride ZX008-1900/EP0215

• CGI-I, globally and for specific domains, as assessed by parent/caregiver

Assessments by the investigator (or designee) should be performed by the same rater for each subject whenever possible. If the rater changes permanently, a new baseline Clinical Global Jithori Zation Impression – Severity (CGI-S) (refer to Appendix 3 of the Clinical Study 1900/EP0215 Protocol Amendment 4.0) should be established (see Section 7.1.2 of the Clinical Study 1900/EP0215 Protocol Amendment 4.0). The same parent/caregiver should perform each assessment. If the same parent/caregiver is not available, the assessment should be skipped.

INVESTIGATIONAL PLAN 4

4.1 **Overall Study Design and Plan**

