9.7 Vital Signs, Weight and BMI

Vital signs data are scheduled to be documented at each clinic visit according to the Schedule of Assessments for Subjects (refer to Section 16.1 of this SAP, Amendment 4.0, Amendment 4.1-FR, Amendment 4.1-UK tables). Vital sign measurements will include blood pressure, heart rate, temperature, and respiratory rate and observed values and changes from Baseline will be summarized and reported in tables for the SAF population.

Body weight and height are scheduled for collection at each clinic visit according to the Schedule of Assessments for Subjects (refer to Section 16.1 of this SAP, Amendment 4.0, Amendment 4.1-FR, and 4.1-UK tables). BMI will be recalculated during programming as weight (kg) / height (m)².

Age and sex-based z-scores for height and weight at each assessment will be determined using growth charts available from the Centers for Disease Control (CDC) and the World Health Organization (WHO). Details of the data sources are available at the following website, updated 09Jan2023.

https://www.cdc.gov/nccdphp/dnpao/growthcharts/resources/sas.htm

The Z-scores will be determined based on the subject's age in months at the date of assessment. For subjects with an incomplete birth date due to country requirements, January 1st of the provided year of birth will be assumed to be the date of birth. Age (in months) will be recalculated at each visit as [(date of visit) - (date of birth)]*12/365.25 for the calculation of z-scores. The z-scores will be determined only for subjects whose age at assessment is ≤ 20 years of age. Z-scores will be included in selected tables overall and split by syndrome (Dravet syndrome or LGS).

For weight the occurrence of at least a $\geq 7\%$ gain/reduction or $\geq 10\%$ gain/reduction from Baseline will be summarized in tables and reported for the SAF Population (overall and split by syndrome) by visit and at any time during the study.

Spaghetti plots will be used to summarize changes in weight. Plots of z-scores will be produced for each subject with $a \ge 7\%$ and $\ge 10\%$ change from Baseline in weight and will be displayed by visit.

For each vital signs, height, weight, and BMI parameter, observed values at each visit and change from baseline at each post-baseline visit will be summarized with descriptive statistics in a table for the SAF Population.

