Listings of the markedly abnormal vital signs, weight, and BMI results will be provided by syndrome (Dravet syndrome or LGS). Markedly abnormal values are summarized in the table below:

Version 4.0 Confidential Page 32 of 59

Zogenix International Limited, a wholly owned subsidiary of UCB 27 October 2023

Statistical Analysis Plan Fenfluramine Hydrochloride ZX008-1900/EP0215

Statistical Allarysis				ZA008-1900/EF0213
Parameter	Age Group	Abnormally	Abnormally	Change Criteria
	(Years)	Low	High	
Weight (kg)	All			≥7% reduction/gain from baseline
	All			≥10% reduction/gain from baseline
Heart Rate (beats /minute)	2	< 87	> 150	Absolute Change from baseline > 20 bpm
	3	< 82	> 146	Absolute Change from baseline > 20 bpm
	4-5	< 77	> 142	Absolute Change from baseline > 20 bpm
	6-7	< 71	2137	Absolute Change from baseline > 20 bpm
	8-11	< 66	C 129	Absolute Change from baseline > 20 bpm
	12-14	₹61 ×0	\$121	Absolute Change from baseline > 20 bpm
	15-17	S57 et	> 115	Absolute Change from baseline > 20 bpm
	18-100	260	> 100	Absolute Change from baseline > 20 bpm
SBP (mmHg)	2-4	< 85	> 100	Absolute Change from baseline > 20 mmHg
Chu ₆	5-11	< 90	> 110	Absolute Change from baseline > 20mmHg
900 36,	12-17	< 100	> 120	Absolute Change from baseline > 20 mmHg
	18-100	< 90	>130	Absolute Change from baseline > 20 mmHg

Version 4.0 Confidential Page 33 of 59

Zogenix International Limited, a wholly owned subsidiary of UCB 27 October 2023
Statistical Analysis Plan Fenfluramine Hydrochloride ZX008-1900/EP0215

Parameter	Age Group	Abnormally	Abnormally	Change Criteria
	(Years)	Low	High	
DBP (mmHg)	2-4	< 40	> 64	Absolute Change from baseline > 10 mmHg
	5-11	< 51	> 75	Absolute Change from baseline > 10 mmHg
	12-17	< 61	> 80	Absolute Change from baseline > 10 mmHg
	18-100	< 60	> 85	Absolute Change from baseline > 10 mmHg
BMI (kg/m²)	2-17	≤ 20	≥ 25	13,013
	18-100	≤ 20	>30	
Respiration Rate (breaths/min)	2	< 18	> 42	
	3	< 18	≥ ₄₀ <	
	4-5	₹ 17 × O	€37	
	6-7	EBO TE	> 35	
	8-11	< 15	> 31	
	12-14	Q 13	> 28	
	15-17	< 13	> 26	
N.C	18-100	< 12	> 20	
Temperature (Celsius)	АН	≤ 36	≥ 38	> 4

Vital signs, weight, height, z-scores, and BMI data will be presented for the SAF Population in a listing. Electrocardiogram and ECHO Analysis of ECGs and Doppler ECHOs will be included in a separate CV SAP from ERT (formerly Biomedical Systems).

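### In growing children the weight flag and the trigger for z-score plots use raw percent change, so no output singles out a child whose weight stays flat; the single BMI band for ages 2–17 does not discriminate either.

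*SAP*

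**What the plan says.** SAP 3.3.1 names "Body weight/height" as a safety endpoint. SAP 9.7 then handles weight in two ways that are not connected.

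- **Z-scores.** Age- and sex-based z-scores for weight and height are derived at each assessment from named growth charts: "The z-scores will be determined only for subjects whose age at assessment is ≤ 20 years of age". They are reported at group level ("Z-scores will be included in selected tables overall and split by syndrome") and at subject level ("Vital signs, weight, height, z-scores, and BMI data will be presented for the SAF Population in a listing"). No threshold on a z-score or on its change is given.
- **Raw percent change.** Every subject-level weight criterion is a change of 7% or 10% from the Visit 1 baseline, in either direction. It drives the occurrence tables ("gain/reduction from Baseline will be summarized in tables and reported for the SAF Population"), the Weight rows of the markedly abnormal table ("≥7% reduction/gain from baseline" and the 10% counterpart, one rule for all ages) and the choice of subjects for individual z-score plots ("Plots of z-scores will be produced for each subject with" a change of that size).

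The same table sets limits by age for the other measures. Heart rate and respiration rate each have seven bands within ages 2–17, and systolic and diastolic pressure have three each. BMI has one band for ages 2–17: low at 20 or below, high at 25 or above. The adult low limit is also 20 or below.

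**The concern.** A fixed percent change from baseline suits adults, whose expected change is near zero. In a child the expected change is positive and accumulates over three years. The gain side of the flag then records ordinary growth, and the child whose weight stands still, who should draw attention, sits at 0% and is never flagged. The z-score plots would show the problem, but the same percent rule selects who gets one.

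A BMI flag could have been a second chance to catch such a child. It is not, if most young children already meet the low limit at baseline.

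The primary objective is long-term safety, and the youngest analysis age group is 2 to under 6 years. Protocol 1.5.1 lists the adverse events seen in at least 10% of subjects in the long-term Dravet extension, and the list includes decreased appetite ("blood glucose decreased, decreased appetite, diarrhea, ear infection"). Slowed growth is therefore a plausible signal. These flags are reporting devices and do not control care. The stake is whether the report can show the signal at subject level.

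**Working it through.** The documents give no figure to reproduce here. The check applies the SAP's rules literally to growth paths. Visit days come from SAP 7.4, with t = days/365.25: Day 360 = 0.986 y, Day 720 = 1.971 y, Day 1080 = 2.957 y. Growth rates and BMI distributions are not in the documents and are shown as ranges.

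**1. Smallest steady gain that meets the gain flag (no growth assumption).** g = (1 + threshold)^(1/t) − 1.

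| By | +7% | +10% |
|---|---|---|
| Day 1080 | 1.07^(1/2.957) − 1 = 2.3% a year | 3.3% a year |
| Day 720 (end of treatment in Denmark) | 3.5% a year | 5.0% a year |

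**2. First scheduled visit at which a child growing as expected is flagged (assumed gain 5% to 15% a year).**
- At 5% a year: +4.9% at Month 12, +7.5% at Month 18, +10.1% at Month 24. Flagged at +7% from Month 18 and at +10% from Month 24.
- At 15% a year: +7.1% at Month 6, +14.8% at Month 12. Flagged at +7% from Month 6 and at +10% from Month 12.

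**3. Shortfall of a child with flat weight.** Raw change is 0% at every visit, so neither threshold is met. Shortfall against expected weight = 1 − 1/(1+g)^t.

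| Visit | g = 5% | g = 15% |
|---|---|---|
| Month 12 | 4.7% | 12.9% |
| Month 24 | 9.2% | 24.1% |
| Month 36 | 13.4% | 33.9% |

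The unplotted group is every child who stays within 7% of baseline throughout. One who ends at +6.9% on Day 1080 has a shortfall of 1 − 1.069/(1+g)^2.957 = 7.5% to 29.3%.

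**4. The same flat path on the z scale.** Fall = ln(1+g) × years/s, where s is the SD of log weight at a given age. Assuming g of 5% to 12% and s of 0.12 to 0.20, the fall is 0.24 to 0.94 at 12 months, 0.49 to 1.89 at 24 months and 0.73 to 2.83 at 36 months. A z-score rule can therefore see what the percent rule cannot.

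**5. BMI limit of 20.** By algebra alone, a child 1.10 m tall must weigh more than 20 × 1.10² = 24.2 kg to escape the low flag; at 1.30 m, more than 33.8 kg. For the share flagged, assume a normal distribution: P = Φ((20 − mean)/SD).

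| Assumed group | Mean | SD | Flagged low |
|---|---|---|---|
| Young children | 15.5 | 1.5 / 3 | 99.9% / 93% |
| Young children | 17.5 | 1.5 / 3 | 95% / 80% |
| Adolescents | 19 | 3 / 4 | 63% / 60% |
| Adolescents | 21 | 3 / 4 | 37% / 40% |

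Example: at 1.10 m and BMI 16, weight is 16 × 1.10² = 19.4 kg. If weight stays there while height rises 4 to 6 cm a year, BMI after three years is 19.36/1.22² = 13.0 to 19.36/1.28² = 11.8. A second child whose BMI stays at 16 is also low at every visit. The flag does not tell them apart.

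**The case against.** The strongest reply is that nothing is hidden. Z-scores are derived for every eligible subject, listed, and included in selected tables. Weight, height and BMI changes are summarized by visit, and spaghetti plots show weight change. Table shells are not part of the documents and might already separate gains from reductions or tabulate z-score change. Actual loss of 7% or more is flagged, and the protocol's withdrawal criterion also concerns weight loss. Most growing children will cross +7% and so get a plot; only those within 7% throughout do not, and that group is not sized. The largest shortfalls need zero gain for 36 months and 15% annual expected growth. BMI is not itself a named endpoint, and its table is damaged in extraction.

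Much of this is fair as a limit. A careful reader could find a faltering child by hand. The size of the affected group is unknown, and expected growth may be lower in this population than assumed. The BMI row should be checked against the original, although its limits read cleanly.

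What survives is the narrower claim. No pre-specified output singles out faltering growth: the listing carries no z-score flag, the spaghetti plots have no stated age reference, and the one subject-level z-score display is selected by a rule that a flat weight cannot meet.

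**Conclusion.** The concern holds. That a flat-weight child is neither flagged nor plotted follows from the SAP's rule alone, as does the 2.3% a year that is enough to cross +7% by Day 1080. The size of the shortfall missed (13% to 34% at Month 36) rests on assumed expected growth of 5% to 15% a year. The BMI over-flagging (about 80% to 99.9% in young children, 37% to 63% in adolescents) rests on assumed normal distributions; it is strong for young children and weaker for adolescents. That BMI has a single paediatric band sharing the adult low limit is in the table itself, subject to checking that row against the original.

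No estimate is biased and no care decision depends on these flags. But for a named safety endpoint in a long-term safety study, the flags in children mostly mark growth or body size. This should be changed before the final outputs are produced.

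**What to change.** - For subjects aged up to 20, pre-specify a criterion on fall from baseline in weight-for-age and height-for-age z-score (for example 0.5 and 1.0, for the sponsor to confirm). Tabulate it by visit and at any time, and use it to select subjects for z-score plots.
- State how the criterion treats subjects who pass age 20 on study, and those whose birth date is set to 1 January, since their derived age can be off by up to a year.
- Report raw percent gains and reductions in separate rows, and keep raw percent change as the flag above age 20.
- For ages 2–17, replace the 20/25 BMI limits with age- and sex-referenced limits and name the reference, because the SAP names a growth-chart source for height and weight only.

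The cost is SAP wording and some reprogramming. Weight and height z-scores are already derived, so no new data are needed. The downsides are a paediatric rule that differs from the adult one and a BMI reference to be specified.

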Both Study 1 and Study 1504 Cohort 2 met the primary efficacy endpoint and all key secondary efficacy endpoints. In Study 1, subjects randomized to ZX008 0.8 mg/kg/day achieved a reduction in mean monthly (28 days) baseline-adjusted CSF of 62.3% compared to placebo (P < 0.001) and subjects randomized to ZX008 0.2 mg/kg/day achieved a 32.4% reduction compared to placebo (P = 0.021). In Study 1504 Cohort 2, in which all subjects were taking STP, subjects randomized to ZX008 0.5 mg/kg/day achieved a 54.0% reduction compared to placebo (P < 0.001).

Controlling for multiplicity with a hierarchical testing procedure, all key secondary endpoints were met in both studies, for ZX008 0.8 mg/kg/day and 0.2 mg/kg/day groups (Study 1) and ZX008 0.5 mg/kg/day (Study 1504 Cohort 2). In Study 1, the proportion of subjects achieving a \geq 50% reduction from Baseline in CSF was 67.5% for the ZX008 0.8 mg/kg/day group, and 38.5% for the 0.2 mg/kg/day group, with both groups being statistically significantly different from placebo (12.5%; P < 0.001 and P = 0.009, respectively). In Study 1504 Cohort 2, 53.5% of subjects randomized to ZX008 0.5 mg/kg/day compared to 4.5% of subjects randomized to placebo achieved a \geq 50% reduction from Baseline in CSF (P <0.001).

ZX008 was generally well tolerated in both Study 1 and Study 1504 Cohort 2. Though more subjects randomized to ZX008 than to placebo reported TEAEs during the double-blind studies, the percent of subjects with serious TEAEs was similar. Additionally, the adverse events observed in the program were either already known to be associated with fenfluramine, are common to many other antiepileptic drugs being prescribed to these patients, and/or are common to the age group and population studied. Specifically, the most common adverse events seen were diarrhea, fatigue, pyrexia, upper respiratory tract infection, blood glucose decreased, weight decreased, decreased appetite, lethargy and tremor. No valvular heart disease, pulmonary arterial hypertension or abnormal valve structure was observed in any subject at any time during the entire program.

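### The SAP's markedly abnormal BMI limits are not age-specific for ages 2–17, so the low flag is uninformative in young children

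*SAP*

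**What the plan says.** The table of markedly abnormal values in SAP section 9.7 has two BMI rows. The paediatric row reads "BMI (kg/m²) 2-17 ≤ 20 ≥ 25". The row for ages 18–100 also sets the low limit at 20 or below and sets the high limit above 30. Neither row has a change-from-baseline criterion.

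The table drives one output: "Listings of the markedly abnormal vital signs, weight, and BMI results will be provided by" syndrome.

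Other parameters in the table are split by age within childhood. Heart rate and respiration rate each use 2, 3, 4–5, 6–7, 8–11, 12–14 and 15–17 years. Systolic and diastolic pressure use 2–4, 5–11 and 12–17; the first diastolic row is "DBP (mmHg) 2-4 < 40 > 64". Temperature has one band for all ages, and weight has only percentage change from baseline.

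The section also adjusts growth for age elsewhere: "Age and sex-based z-scores for height and weight at each assessment will be determined using growth charts", for participants aged 20 or younger at the assessment. No such score is stated for BMI, which is computed by the plain formula: "BMI will be recalculated during programming as weight (kg) / height (m)²".

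**The concern.** BMI in childhood depends on age, as do the parameters that the table splits into age bands. Giving a 2-year-old the adult lower limit means that the flag may mark ordinary young children rather than thin ones. It may also mark as low a child who is heavy for age.

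This matters because weight is a known issue with this drug. Protocol section 1.5.1 lists among the most common adverse events of the controlled Dravet trials "blood glucose decreased, weight decreased, decreased appetite, lethargy and tremor", and decreased appetite recurs among the events in at least 10% of participants in Study 1503. Body weight and height are a safety endpoint in Protocol section 2.3.1 and SAP section 3.3.1. In the markedly abnormal table, BMI is the only body-size measure with absolute low and high limits. A reader looking there for underweight children would find a listing that cannot pick them out.

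**Working it through.** The plan states no flag rate, so there is no figure to reproduce. Two checks apply.

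**1. Arithmetic from the SAP's own formula (no outside data).** A child escapes the low flag only if weight > 20 × height², and is flagged high only if weight ≥ 25 × height².

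| Height | Must exceed, to avoid low flag | Needed for high flag |
|---|---|---|
| 0.85 m | 20 × 0.7225 = 14.45 kg | 18.1 kg |
| 1.00 m | 20 × 1.00 = 20.0 kg | 25.0 kg |
| 1.10 m | 20 × 1.21 = 24.2 kg | 30.25 kg |
| 1.20 m | 20 × 1.44 = 28.8 kg | 36.0 kg |

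With no change criterion, a child whose BMI stays at or below 20 is listed at every visit.

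**2. Share flagged, under an assumed distribution.** The documents give no paediatric BMI distribution, so the following is an assumption shown over a range. Take BMI as lognormal with median M and coefficient of variation CV, so σ = √ln(1 + CV²). Then P(low) = Φ[ln(20/M)/σ] and P(high) = 1 − Φ[ln(25/M)/σ].

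Example with M = 17 and CV = 20%: σ = √ln(1.04) = 0.198; ln(20/17) = 0.1625; 0.1625/0.198 = 0.82; P(low) = 79.4%.

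| Median BMI | Low, CV 8% | Low, CV 20% | High, CV 8% to 20% |
|---|---|---|---|
| 15 | 100.0% | 92.7% | 0.0–0.5% |
| 16 | 99.7% | 87.0% | 0.0–1.2% |
| 17 | 97.9% | 79.4% | 0.0–2.6% |
| 18 | 90.6% | 70.3% | 0.0–4.9% |
| 20 | 50.0% | 50.0% | 0.3–13.0% |
| 22 | 11.6% | 31.5% | 5.5–25.9% |

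A normal approximation agrees: mean 15.5 and SD 1.5 gives Φ(3.0) = 99.9%; mean 16 and SD 2 gives Φ(2.0) = 97.7%; mean 17 and SD 2.5 gives Φ(1.2) = 88.5%.

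**Direction of the error.** At mean 16 and SD 2, the cut-off of 20 lies two SDs above the mean, since (20 − 16)/2 = 2. Every child up to that point is labelled low, including those well above average for age.

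**What the flag misses.** Take a child at BMI 16 and height 1.00 m, so weight is 16 × 1.00² = 16 kg. If the child grows to 1.10 m with no weight gain, BMI falls to 16/1.21 = 13.2. The low flag is set at both visits, so it does not register the fall.

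**The case against.** The strongest case on the other side is that little depends on this flag. Section 9.7 also plans:

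- age- and sex-based weight and height z-scores up to age 20, in selected tables overall and by syndrome;
- tables of weight gain or reduction of at least 7% and at least 10%, by visit and at any time;
- spaghetti plots of weight change, and z-score plots for participants who reach those weight changes;
- descriptive statistics for BMI and its change from baseline;
- a full listing of weight, height, z-scores and BMI.

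Weight-related adverse events also appear in the TEAE tables. BMI is not a named safety endpoint, and no test or stopping rule uses the flag. Protocol section 4.4 leaves withdrawal for weight loss to the investigator's determination.

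Most of this stands. A reader might infer that real under- or overweight cannot be seen in this study; the outputs above show that it can. A reader might also infer that the listing would contain almost every participant. That fails too: the low share drops at the higher medians that might apply to older children, and adults are enrolled.

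Two limits remain. Separate weight and height z-scores are not a measure of weight for stature at a given age. And the child above, who grows without gaining weight, reaches no percentage weight-change threshold, so gets no individual z-score plot. The falling weight z-score would still be in the full listing.

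Table damage in the PDF text is another possible explanation, since some nearby heart-rate cells are garbled. Both BMI rows are legible, however, and agree on the lower limit.

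**Conclusion.** The point holds as a defect of one descriptive listing. One fixed band covers ages 2–17, with the adult lower limit and without the age-banding given to heart rate, blood pressure and respiration rate. The weight thresholds are exact arithmetic.

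The rate is conditional. For young children with a median or mean BMI of 15–17 and moderate spread (CV 8–20%), about 79–100% of assessments would be listed as abnormally low and at most 2.6% as high. On that assumption the low flag does not separate thin from ordinary young children, and it includes some who are heavy for age. The share is about 50% at a median of 20 and 12–32% at 22, so the failure is concentrated in the younger part of the band. The sponsor can replace the assumption with its own baseline BMI data.

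No endpoint estimate or test changes. The case for acting is that a stated rule gives a misleading label on a drug with known weight effects, and that correction is cheap.

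**What to change.** In the SAP 9.7 table, replace the fixed BMI limits for ages 2–17 with BMI-for-age-and-sex z-score limits from the growth-chart source already used for height and weight. State the low and high cut-offs in advance, for example z < −2 and z > +2. If BMI z-scores followed the reference population, each tail would then hold about 2.3% of assessments (Φ(−2)).

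Keep the fixed kg/m² limits in the existing 18–100 row. The height and weight z-scores run to age 20, so the text should say that the BMI z-score rule stops at 17; ages 18–20 then fall under one rule only. Choose the row by age at assessment, as the z-scores already do.

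The SAP names the growth-chart source for height and weight only, and the documents do not show whether it supplies BMI-for-age. If it does not, drop the paediatric BMI flag and rely on the planned z-score and weight-change outputs.

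The cost is a wording change and one extra derived variable, or none if the flag is dropped. No new data are needed. On the assumptions above, the paediatric BMI listing would become much shorter.
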